## 14.6 Investigator Compliance

The investigator will conduct the study in compliance with the protocol provided by the sponsor and in accordance with all relevant regulatory guidelines and requirements.

Modifications to the protocol should not be made without the agreement of the investigator and sponsor. The sponsor will submit all protocol modifications to the appropriate regulatory authority in accordance with applicable regulations. All protocol modifications require written IEC/IRB approval/favorable opinion, except in the case of an immediate hazard to subjects.

If an immediate deviation from the protocol is required to eliminate an immediate hazard to subjects, the investigator must contact the sponsor or assigned CRO, if possible, to discuss the planned course of action. The investigator must thoroughly document any departure from the protocol and submit appropriate documentation to the sponsor without delay.

# **16 APPENDICES**

FST	Fitzpatrick skin type

CCI

ITT	Intent to treat
MedDRA	Medical Dictionary for Regulatory Activities
N	Number of non-missing observations
PP	Per Protocol
PROC MI	SAS multiple imputation procedure
PT	Preferred term
SAE	Serious Adverse Event
SAP	Statistical Analysis Plan
SAS	Statistical Analysis System®
SD	Standard deviation

CCI

SOC	System organ class
SP	Safety population
SSQ	Subject Satisfaction Questionnaire
TEAE	Treatment Emergent Adverse Event
TESAE	Treatment-emergent serious adverse event
TFL	Tables, Figures, Listings

1 General and Technical Aspects

The objective of this statistical analysis plan (SAP) is to specify the final statistical analyses with appropriate detail and precision to serve as a guideline for statistical programming and creation of tables, figures, and listings for clinical study protocol M960101003, dated 22-Jul-2021, version 5.0 (Amendment 4).

All programs will be written using SAS version 9.4 or higher. A preferred font size of 9 points, minimum font size of 8 points with a unique font size for the whole document required will be used for the tables and figures in Section 14. For listings, a standard font size of 9 points above will be used to produce the output in A4 format. Individual SAS programs will be written for all tables, figures, and listings. All outputs will be transferred into PDF files. These PDF files will be generated as needed to populate the subsections of Section 14 and Section 16.2 for the clinical study report. Each output file will include the corresponding table of contents, preceding the content of the file.

The Merz standard Tables, Figures, and Listings (TFLs) for medical devices, version 2.0, dated 18-Feb-2020, will be applied and adapted to study specific requirements as laid down in the clinical study protocol and any amendments. These mock TFLs will serve as study-specific output specifications for statistical programming.

Special attention will be paid to planning and performance of quality control measures. Risk scores based on assessments of complexity and impact of errors and quality control measures for statistical programming (including analysis datasets and TFLs) will be documented in the quality control plan for the creation of statistical output.

2 Clinical Trial Design and Objectives

2.1 Clinical Study Design

This is a 180-day, prospective, evaluator-blind, multicenter, staged, confirmatory study designed to evaluate the safety and effectiveness of the Octave System for improving lines and wrinkles of the décolleté. Approximately 90 subjects will be enrolled at up to ten investigational sites in the United States. All Fitzpatrick skin types (FST) will be eligible for study enrollment. It is estimated that approximately 90% of the total sample size will consist of subjects with FST I, II, or III, and approximately 10% of subjects will be FST IV, V, or VI. Subjects enrolled will be healthy females, aged 35 to 65 years at the time of screening, with moderate to severe fine lines, wrinkles, laxity, and crepiness of the décolleté that is amenable to improvement with non-invasive intervention and is not severe enough for surgical intervention.

In this non-comparative, staged, confirmatory study, investigators and subjects will not be blinded to treatment, subjects will not be randomized, and all enrolled subjects will receive a single Octave-Ultherapy treatment of the décolleté tissue with two transducers at energy level 4 CCI [REDACTED]

CCI [REDACTED] and one transducer at energy level 3 CCI [REDACTED]

In Stage 1, an initial cohort of subjects will be enrolled, safety data will be assessed up to Week 2, and subjects will participate until Stage 1 study end at Day 90. In Stage 2, all enrolled subjects will be followed for 90 days or 180 days if reconsented for extended participation. In addition, to reduce potential bias associated with using only treated-subject photographs for evaluation, photographs of approximately 30 untreated individuals, who meet selected appearance criteria, will be collected at two different time points and subsequently paired for evaluation by the independent, blinded evaluators. Using this 3:1 ratio of treated subjects to untreated individuals, image sets of these untreated individuals will be randomly distributed among the pre- and post-treatment image sets of the treated subjects and presented to the blinded evaluators. For the primary effectiveness endpoint, the “baseline” photograph will be identified as “Photograph 1”, and the independent evaluators will be blinded

to the randomly distributed treated versus untreated status of the comparator Photograph 2 (i.e., Day 90 post-treatment among treated subjects or post-baseline for untreated individuals). The same photographic assessment will be used for the secondary effectiveness endpoint with the comparator Photograph 2 collected at Day 180 post-treatment.

Study subjects will have approximately 4 in-office study visits, including screening, baseline/treatment, a Day 90 (\pm 7 days) post-treatment visit, and a Day 180 (\pm 14 days) post-treatment visit. Up to five follow-up telephone calls will occur at 3 days (\pm 1 day), 14 days (\pm 3 days), 28 days (+ 3 days), 120 days (\pm 7 days), and 150 days (\pm 7 days) after Octave-Ultherapy treatment. The primary effectiveness endpoint, the proportion of treated subjects with improvement in lines and wrinkles of the décolleté, will be evaluated using a blinded, independent assessment of photographs at post-treatment Day 90 compared to baseline. Improvement is concluded if at least two of three independent, blinded evaluators assess the Day 90 standardized, photographic images as improved compared to baseline photographic images.

Standard safety evaluations, including the incidence of adverse events (AEs) and serious adverse events (SAEs), will be assessed.

2.2 Clinical Study Objectives

The objective of this study is to demonstrate the safety and effectiveness of the Octave System for improving lines and wrinkles of the décolleté.

3 Determination of Sample Size

A responder rate of 70% is assumed for the proportion of subjects with improvement from baseline to Day 90, as defined by the correct selection of the Day 90 standardized, photographic images by two of three independent, blinded evaluators. Monte-Carlo simulations were conducted to obtain sample sizes of evaluable subjects required to achieve an improvement rate of \geq 65% and lower bound of 1-sided 95% confidence interval (CI) above 50%. To achieve this threshold with \geq 85% power, a sample size of 80 evaluable subjects will be required. Assuming a maximum attrition of 10 subjects, approximately 90 subjects will be enrolled. In Stage 1, 10 subjects will be enrolled, while all other subjects will be enrolled in Stage 2. Because a sample size of 80 subjects who complete the full Ultherapy treatment session is required, study enrollment will continue until the required number of treated subjects is achieved.

4 Analysis Sets

The following analysis sets will be defined for the statistical analysis of this clinical study:

4.1 Safety Population (SP)

The Safety Population (SP) includes all subjects who are enrolled and are treated with the Octave System.

4.2 Intent-to-Treat (ITT) Population

The Intent-to-Treat (ITT) population consists of all subjects who are enrolled.

4.3 Per Protocol (PP) Population

The Per Protocol (PP) population consists of all subjects in the ITT population who complete the full Ultherapy treatment session using the Octave System and do not have a major protocol violation. Major protocol deviations will be defined during the Data Review Meeting (DRM).

5 Endpoints for Analysis

5.1 Effectiveness Endpoints

The effectiveness of the Octave System to improve lines and wrinkles of the décolleté will be evaluated using several methods, including qualitative assessment of photographs by three blinded evaluators.

5.1.1 Primary Effectiveness Endpoint

The primary endpoint of the study is the proportion of treated subjects with improvement in lines and wrinkles of the décolleté by comparing photographs taken at Day 90 (post-treatment) with baseline (pre-treatment) photographs. If the subject's screening photograph (Visit 1) is deemed acceptable upon review by the central photography vendor, it will default to the baseline (pre-treatment) photograph and will be used for reference throughout the study.

- Improvement is concluded if at least two of three independent, blinded evaluators assess the Day 90 standardized, photographic images as improved compared to baseline photographic images.
- The success criterion is defined by achieving simultaneously a point estimate $\geq 65\%$ and a lower bound of the one-sided 95% Wilson confidence interval $> 50\%$ for the proportion of treated subjects with improvement.

5.1.2 Secondary Effectiveness Endpoint

- Proportion of treated subjects with improvement in lines and wrinkles of the décolleté by comparing photographs taken at Day 180 (post-treatment) with baseline (pre-treatment) photographs.

CCI

5.2 Safety Endpoints

5.2.1 Secondary Safety Endpoint

Incidence of treatment-emergent adverse events (TEAEs) related to Octave-Ultherapy treatment, as reported throughout the study.

CCI

CCI

6 Statistical Analysis Methods

Adequate descriptive statistics will be provided for each effectiveness and safety evaluation. Continuous variables (values and changes from baseline) will be summarized by number of observed values (n obs), number of missing values (n miss), number of imputed values (n imp, where applicable), mean, standard deviation, median, quartiles, minimum and maximum (i.e., metric statistics). Mean, quartiles, and median will be reported to one decimal place more than the data were collected, for the standard deviation two decimal places more will be displayed; for derived data, the number of decimal places will explicitly be given in the sections below.

Categorical variables will be summarized by frequencies and percentages (n, %) per category where the denominator will be chosen according to the adequate analysis population (i.e., frequency statistics). Frequency tables will include the number of missing values. Percentages will be calculated using the denominator of all subjects in a specified population. Percentages will be calculated using the number of subjects with non-missing data at the corresponding visit as denominator (observed cases). The denominator will be specified in a footnote to the tables for clarification if not otherwise obvious. Percentages will be reported to one decimal place.

Ordered categorical data will be summarized by quantitative and frequency statistics.

Shift tables, confidence limits (95%, two-sided), and descriptive p-values, where appropriate will be given, where appropriate.

Due to the COVID-19 pandemic outbreak, onsite visits might not be performed or only performed as virtual contact. In such cases, quantitative evaluations/assessments will not be performed.

CCI

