and one transducer at energy level 3 . In Stage 1, an initial cohort of subjects will be enrolled, safety data will be assessed up to Week 2, and subjects will participate until Stage 1 study end at Day 90. In Stage 2, all enrolled subjects will be followed for 90 days or 180 days if reconsented for extended participation. In addition, to reduce potential bias associated with using only treated-subject photographs for evaluation, photographs of approximately 30 untreated individuals, who meet selected appearance criteria (Section 11.2.1.1.1), will be collected at two different time points and subsequently paired for evaluation by the independent, blinded evaluators. Using this 3:1 ratio of treated subjects to untreated individuals, image sets of these untreated individuals will be randomly distributed among the pre- and posttreatment image sets of the treated subjects and presented to the blinded evaluators. For the primary effectiveness endpoint, the "baseline" photograph will be identified as "Photograph 1", and the independent evaluators will be blinded to the randomly distributed treated versus untreated status of the comparator Photograph 2 (i.e., Day 90 post-treatment among treated subjects or post-baseline for untreated individuals). The same photographic assessment will be used for the secondary effectiveness endpoint with the comparator Photograph 2 collected at Day 180 post-treatment. Additional information on the methodological plan, detailing photograph collection through subsequent presentation to

blinded evaluators, will be provided in a supporting document, developed collaboratively between the sponsor and the photography vendor.

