#### 9 STUDY POPULATION AND RESTRICTIONS

#### 9.1 Number of Subjects and Sites

Approximately 80 evaluable subjects, who complete the full Ultherapy treatment session using the Octave System, are planned for this study. Assuming a screen failure rate of 20%, approximately 113 subjects will be screened; assuming attrition of 10 subjects, approximately 90 subjects are planned for enrollment/treatment. All subjects will sign and date the ICF before any study-related procedures are undertaken.

In Stage 1, 10 subjects will be enrolled at a minimum of two investigational sites (maximum: 6 sites) in the United States, while all other subjects will be enrolled in Stage 2. Number of investigational sites will not exceed ten in total. During Stage 1, Week 2 safety data for the first 10 treated subjects will be evaluated. All 10 subjects enrolled in Stage 1 will participate until Stage 1 study end at Day 90. In Stage 2, all other enrolled subjects will participate for at least 90 days ( $\pm$  7 days), with a maximum duration of 180 days ( $\pm$  14 days) if reconsented for extended participation. Females of all FST are eligible for study participation. In addition, approximately 10% of the enrolled subjects will be categorized as FST IV, V, or VI, and of which 5% will be categorized as FST V or VI.

Subjects who are enrolled and who do not complete the study will not be replaced. Furthermore, the secondary effectiveness endpoin at Day 180 will only be assessed among subjects who reconsent at their Day 90 visit for extended study participation to Day 180.

Photographs of approximately 30 untreated individuals, who meet selected appearance criteria (Section 11.2.1.1.1), will be collected at two different time points, between 1 day and 1 week apart; these photographs will be subsequently paired for evaluation by the independent, blinded evaluators.

To confirm the presence of appropriate anatomy at the intended depth of treatment (see Inclusion Criterion #3 in Section 9.2.1), the treating investigator will use the Octave System's supplemental imaging mode to visualize the dermal and subdermal layers of tissue. For example, subjects with bone, rather than soft tissue, at the intended treatment depth would be considered screen failures and would not be eligible for enrollment. [16]

Additional information regarding subject enrollment is provided within the sample size justification (Section 13.1).

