## 11 STUDY PROCEDURES

#### 11.1 Visit Schedule

The investigation activities and visit schedule are detailed in the Schedule of Events

The purpose of the screening visit (Visit 1) is to determine subject eligibility for study participation and must be completed no more than 21 days prior to Day 1 (Visit 2). Informed consent is to be obtained at the screening visit, and the reviewing/recording of AEs begins upon ICF signature. Subject demographics, including FST should be recorded in the eCRF, and a subject-reported medical history is acceptable.

Note: Additionally, for each site, approximately the first four to five subjects with moderate to severe fine lines, wrinkles, laxity, and crepiness of the décolleté, as enrolled by the investigator, will be confirmed for study-appropriate lines and wrinkles of the décolleté via an independent photographic reviewer.

In addition to the activities listed in the Schedule of Events

- At Visit 2 (Day 1), prior to performing the investigator's skin examination, the subject must wash the treatment area to remove any moisturizers/emollients, makeup, bronzing agents, etc. on the neck/décolleté region, if necessary.
- study personnel should schedule follow-up phone call(s) and Visit 3.
- At Visit 3, subjects will be requested to reconsent for extended study participation to 180 days. If reconsented, study personnel should schedule follow-up Day 120 and Day 150 phone call(s) and Visit 4.
- All required subject-related, pre-treatment procedures and assessments should be completed before the administration of oral or IM pain medication (Section 10.5.1.2).
- After administration of the pain medication, study personnel should verify all study-specific treatment settings on the Octave System and prepare study-specific materials needed for treatment (e.g., ultrasound gel). Study personnel should prepare inhaled nitrous oxide/oxygen mixture for potential use, if available.

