6.2 Safety Endpoints

All safety evaluations will be summarized for observed values in the SP.

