6.2.1 Adverse Events

All AEs will be coded according to the Medical Dictionary for Regulatory Activities (MedDRA) version in effect at the time the database is closed.

Only treatment-emergent AEs (TEAEs) will be analyzed, which are defined as AEs with onset or worsening at or after the first administration of study treatment. In this regard, an AE, with onset prior to treatment, that worsens at or after first administration of study treatment must be documented as a new TEAE with onset at the time of worsening.

An overall summary of AEs will be provided for the following:

- Any AEs;
- Any non-TEAEs;
- Any TEAEs;
- Any treatment-related TEAEs;
- Any serious TEAEs;
- Any serious treatment-related TEAEs;
- Any TEAEs leading to discontinuation;
- Any treatment-related TEAEs leading to discontinuation;
- Any fatal TEAEs, and
- Any treatment-related fatal TEAEs.

Incidence will be provided for the following classes of AEs:

- TEAEs, subjects with TEAEs and number of TEAEs by MedDRA system organ class (SOC) and preferred term (PT);
- TEAEs, subjects with TEAEs by PT;
- Non-TEAEs, subjects with Non-TEAEs and number of Non-TEAEs by SOC and PT;
- Non-serious TEAEs, subjects with TEAEs and number of TEAEs by SOC and PT;
- TEAEs by maximum severity (mild, moderate, severe), subjects with TEAEs by PT;

- TEAEs by worst causal relationship (related, not related), subjects with TEAEs by PT;
- TEAEs by worst outcome, subjects with TEAEs by PT;
- TEAEs by affected treatment area, subjects with TEAEs by PT;
- TEAEs by maximum duration (1-3 days, 4-7 days, 8-14 days, ≥ 15 days), subjects with TEAEs by PT;
- TEAEs by maximum duration and maximum severity, subjects with TEAEs by PT;
- Related TEAEs, subjects with TEAEs and number of TEAEs by PT and SOC;
- Serious TEAEs, subjects by SOC and PT;
- Related serious TEAEs, subjects by SOC and PT;
- Serious TEAEs, listing of subjects (in case of more than 15 serious TEAEs respective table by PT and SOC will be provided); and
- Related serious TEAEs, listing of subjects (in case of more than 15 related serious TEAEs respective table by PT and SOC will be provided).

All tables will be sorted by descending frequencies in Preferred Terms (within SOCs).

The duration of AEs will be calculated by the difference of start and stop day plus 1.

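### Related-TEAE incidence puts subjects followed to Day 90 and to Day 180 over one denominator, so it is not a 180-day incidence and it understates the contribution of late-onset events

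*SAP*

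**What the plan says.** The endpoint is "Incidence of treatment-emergent adverse events (TEAEs) related to Octave-Ultherapy treatment, as reported throughout the study" (SAP 5.2.1; Protocol 7.2.2.1 agrees). SAP 6.2.1 defines TEAEs as "AEs with onset or worsening at or after the first administration of study treatment", which fixes a start but no common end day.

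The analysis set is the same for every safety table: "All safety evaluations will be summarized for observed values in the SP" (SAP 6.2). SAP 4.1 defines that set: "The Safety Population (SP) includes all subjects who are enrolled and are treated with the Octave System". The general rules in SAP Section 6 give the denominator: "Percentages will be calculated using the denominator of all subjects in a specified population". The sentence after that gives a second rule, based on non-missing data at a visit. It does not fit adverse events, which are not tied to a visit.

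Follow-up differs by design. Protocol 9.1: "All 10 subjects enrolled in Stage 1 will participate until Stage 1 study end at Day 90". Protocol 8.1: "In Stage 2, all enrolled subjects will be followed for 90 days or 180 days if reconsented for extended participation". The choice is made at the Day 90 visit: "At Visit 3, subjects will be requested to reconsent for extended study participation to 180 days" (Protocol 11.1). Protocol 11.2.2.1 and 12.1.1 end adverse event observation at the subject's last study visit.

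Elsewhere the SAP does allow for the two follow-up lengths. After Day 90, visit attendance is expressed relative to reconsented subjects, and the Day 180 effectiveness endpoint is restricted to them (SAP 6.1.2).

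**The concern.** A subject whose last visit is at Day 90 generally cannot add a later event to the numerator but stays in the denominator. Even a related serious event after the observation period, which must still be reported, would generally stay outside the study database (Protocol 12.2.2). The pooled figure is therefore an incidence over mixed follow-up. It describes neither 90 days nor 180 days.

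Early events are unaffected apart from ordinary dropout. What suffers is the safety information that the extension was added to provide. The list of TEAE tables in SAP 6.2.1 splits by severity, duration, relationship, outcome and treatment area. In the visible text it does not split by onset period or reconsent status, and no person-time rate or censored cumulative incidence is specified. A reader who takes the endpoint as a 180-day incidence would be too reassured about late-onset events.

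**Working it through.** The documents give no figure for this endpoint, so there is none to reproduce. The check needs only counts and one assumption.

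**Inputs**
- Treated subjects: about 90 (Protocol 9.1; SAP Section 3).
- Stage 1 subjects, who end at Day 90: 10 (Protocol 9.1).
- Stage 2 subjects: 90 − 10 = 80. This is not the 80 evaluable subjects of the sample size section, which is also 90 − 10 but subtracts attrition.
- Subjects followed past Visit 3, called m: not given. Assumed 80, 60 and 40, which is 100%, 75% and 50% of Stage 2. Dropout during the extension is ignored.

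**Step 1: contribution of late events.** If x subjects have a related event with onset after Visit 3, the pooled table credits x/90. Among those under observation the proportion is x/m. The ratio is (x/90)/(x/m) = m/90. For illustration, x = 3.

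**Step 2: what an interval would do, if one were given.** With zero late events the exact two-sided 95% upper limit is 1 − 0.025^(1/n).

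| Denominator | Factor m/90 | Three late events | Upper limit, zero late events |
|---|---|---|---|
| 90 (pooled) | – | 3/90 = 3.3% | 4.0% |
| 80 | 0.89 | 3/80 = 3.75% | 4.5% |
| 60 | 0.67 | 3/60 = 5.0% | 6.0% |
| 40 | 0.44 | 3/40 = 7.5% | 8.8% |

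**Step 3: effect on the endpoint as defined.** Let e be the incidence by Visit 3 and l the later incidence among those still event-free, taken to be the same whether or not a subject reconsents. With everyone followed to Day 180 the incidence is e + (1 − e)l. The pooled figure is e + (1 − e)l × m/90.
- Assumed e = 30%, l = 5%: full follow-up gives 0.30 + 0.70 × 0.05 = 33.5%. Pooled: 33.1% (m = 80), 32.3% (m = 60), 31.6% (m = 40).
- Assumed e = 5%, l = 5%: full follow-up gives 0.05 + 0.95 × 0.05 = 9.75%. Pooled: 9.2% (m = 80), 7.1% (m = 40).

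The overall figure therefore moves by at most about two percentage points in the first case, where early events dominate. In the second case, at m = 40, it loses roughly a quarter of its value.

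**The case against.** **No bound is planned.** A reader might infer that the plan will publish an upper confidence limit for late related events that is too tight. The documents do not support that. SAP Section 6 has only a general provision for two-sided 95% limits where they suit, and none is named for TEAEs. A limit that is too tight arises only if that provision is applied, or if a reader derives one from x/90. This objection stands.

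**No late-period percentage is planned.** The endpoint is cumulative, so no table will show 3/90 as a late incidence. This also stands. The defect is that the pooled figure gives late events too little weight and that no late-period figure with its own denominator is specified.

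**The effect may be small.** If all of Stage 2 reconsents, the factor is 0.89 and three events read as 3.3% instead of 3.75%. This is correct, and it is why the whole range is shown. The 10 Stage 1 subjects make some dilution certain, however.

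**A reader could reconstruct it.** All adverse events are listed, onset dates are recorded (Protocol 12.1.2) and post-Day-90 attendance is tabulated over reconsented subjects. So late events are not hidden. But a listing does not replace a defined summary of the secondary safety endpoint.

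**Blacked-out text.** Text is missing next to the safety endpoint and after the adverse event section, and SAP 6.2.1 mentions a time period for worst outcome that the visible text does not define. A period split could exist there, so the point is limited to what can be read.

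**Conclusion.** The point holds for the visible text. Related-TEAE incidence mixes 90-day and 180-day follow-up over one denominator, so it is not a 180-day incidence. The contribution of events with onset after Visit 3 is understated by m/90: 0.89 at best, 0.67 with 60 followed, 0.44 with 40, and less if fewer than half of Stage 2 reconsent. These sizes rest on about 90 treated subjects, an assumed reconsent share and no dropout in the extension.

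It would go too far to read this as a material error in overall related-TEAE incidence. That figure moves little if most events are early, although the documents give no event rates that would settle the matter. Safety reporting here is descriptive, with no success threshold in the visible text. The primary effectiveness result and the sample size are unaffected. This is a cheap improvement, not a threat to the trial's conclusions.

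**What to change.** In SAP 6.2.1, report related-TEAE incidence in two windows:

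1. From treatment to each subject's Visit 3, over all Safety Population subjects.
2. From Visit 3 to Day 180, over the reconsented subjects still followed, with that number footnoted as the denominator.

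Use each subject's own Visit 3 date as the cut. The visit window is ± 7 days, so subjects may leave between Day 83 and Day 97, and a fixed Day 90/91 cut would misallocate follow-up. State how to treat events dated on the day of Visit 3 and subjects with no Visit 3. Keep the overall row as supplementary, labelled as mixed follow-up. State whether an interval is given and, if so, base it on each window's own denominator.

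Add a note that subjects in the second window selected themselves by reconsenting. The split corrects the denominator but does not remove that selection.

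The cost is one extra split of tables that already exist. Onset dates are already recorded, and reconsent status is already needed for the attendance table. Protocol Section 13 allows the SAP to be updated before the final database close.
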